6.1.4 Criteria for discontinuing and resuming study treatment

If the platelet has exceeded $400 \times 10^9/L$ during the treatment period, study treatment will be temporarily discontinued. Once the platelet count falls to $< 200 \times 10^9/L$, administration of AMG531 will resume at a reduced dose by one level according to the protocol. Once the platelet count falls to $\leq 50 \times 10^9/L$ during the treatment with reduced dose by one level, dosing will be resumed at the temporarily discontinued dose.

If the platelet has exceeded $200 \times 10^9/L$ during the treatment period, the dose of AMG531 will be reduced to the next lower dose tested. If the temporarily discontinued dose is $1 \mu\text{g/kg}$, treatment will be resumed at the dose of $1 \mu\text{g/kg}$.

Other than the reasons above, investigator can reduce the dose at any time during the study if safety concerns arise.

6.2 Concomitant medications and therapies

6.2.1 Concomitant medications and therapies

Throughout the study period, investigator may prescribe any concomitant medications or therapies deemed necessary to provide adequate supportive care except for those listed in section 6.2.2. Rescue medication is defined as any medication that is administered to raise platelet counts, hemoglobin concentration or neutrophil counts. Rescue medication should only be administered when subjects is at immediate risk except for the case of transfusion. Platelet and RBC transfusions will be allowed during the study period as clinically indicated. Platelet counts, hemoglobin concentration and neutrophil counts determined after administration of rescue medication suspected to affect its level will not be used for the efficacy assessment. For the platelet transfusion, only single donor platelet (SDP) transfusion will be allowed during the study period.

Iron chelator will be allowed during the study period as clinically indicated.

6.2.2 Prohibited medications and therapies

While on study treatment, subjects are not permitted to receive any additional experimental medication or any therapy known or suspected to affect platelet production and AA from the time of enrollment throughout the study period. Examples of prohibited medications or therapies are follows;

- 1) Any investigational agents other than AMG531
- 2) TPO agonist other than AMG531

- 3) Other drugs to treat AA or symptoms associated with AA (e.g., immunosuppressive agents, cyclosporine, growth factors [For the case of G-CSF, its administration is only permitted as a rescue medication to treat infection, and will be prohibited for the purpose of treating AA])
- 4) Any medication known or suspected to affect platelet production
- 5) Hematopoietic stem cell transplantation

6.2.3 Recording concomitant medication and therapy in electronic Case Report Form (eCRF)

All concomitant medication and therapy that a subject received during the period after enrollment through to the end of the study will be recorded on electronic case report form (eCRF) by the investigator with the following information for each concomitant medication and therapy: name of drug, route of administration, duration of treatment and justification for the administration. Agents not intended for medical treatment such as rehydration including saline solution, dissolving solution, or contrast medium for imaging diagnostics are not required to be recorded.

Platelet transfusions given between the period within 56 days (Day -55) prior to the first administration of AMG531 (Day 1) and RBC transfusion given between the period of within 26 weeks (Day -181) prior to the first administration of AMG531 (Day 1) through to the end of study will be recorded in eCRF, including date of each transfusion, volume of transfusion (unit and mL), platelet count or hemoglobin concentration before each transfusion, and reason for each transfusion.

7 ENROLLMENT OF SUBJECTS

Before obtaining written informed consent from a subject, the investigator will examine the characteristics of each subject, as well as results of evaluations performed so far to select subjects who are expected to fulfill all of the inclusion criteria and not to meet any of the exclusion criteria.

The details of the study will be sufficiently explained by the investigator to the selected subjects, and those who agree to participate in the study will provide an informed consent. All subjects who have submitted an informed consent will be identified by subject identification code (SID) assigned by the investigative site and registered to interactive web response system (IWRS). The numbering conventions of SID are as shown below. SID assigned to each subject after obtaining the informed consent will be consistently used till the end of the study.

SID: 531-XX-YY

XX: Investigative site number (refer to the Study Protocol Supplement)

YY: Serial number of subjects given in chronological order of providing informed consent in each investigative site.

Example: SID of the first subject who provided informed consent in ## Hospital (Investigative site number, 01) will be 531-01-01.

The investigator will start treatment of each subject within 7 days after enrollment at an assigned dose.

- 8) One week after last administration of AMG531, or refer to the section 11.1.2 if subject is withdrawn from the study due to safety issues and cannot conduct the scheduled end of treatment visit.
- 9) Four weeks after last administration of AMG531, or refer to the section 11.1.2 if subject is withdrawn from the study due to safety issues and cannot conduct the scheduled end of study visit.
- 10) This cytokine assay will be required only for the patients withdrawn from the study before Week 53.
- 11) Subjects on discontinuation of AMG531 after achieving normal level for 8 consecutive weeks without transfusion (refer to the section 6.1.3.3) can skip even-numbered visit (i.e make bi-weekly visits).
- 12) For those who discontinued the AMG531 after achieving normal level for 8 consecutive weeks without transfusion (refer to the section 6.1.3.3), dosing will be skipped.
- 13) Required only at Week53 before dosing of AMG531

8.2 Observations/assessments/examinations and schedule

8.2.1 Screening examinations

A signed and dated IRB approved informed consent must be obtained before any study specific procedures are performed. Procedures that are part of routine care are not considered as study specific procedures.

The screening period begins on the date of subject signed the IRB approved informed consent and continues until the date of first administration of AMG531. The following screening examination will be conducted within 4 weeks prior to the first administration of AMG531 (Week -4 to Day 1). Retesting during this period may be performed as needed.

Subjects who fail screening will be allowed to be re-screened if a remediable cause for the original screen failure is found.

- 1) Baseline characteristics: date on which the subject is diagnosed with AA, severity of AA (Appendix 2), previous treatments for AA (duration and sort of treatment), baseline platelet count, platelet transfusion in the previous 8 weeks prior to the first administration of AMG531 (Day -55 to Day 1), RBC transfusion in the previous 26 weeks prior to the first administration of AMG531 (Day -181 to Day1), concomitant medications, medical history, current complications, date of birth, gender, weight, and height, baseline platelet count according to the protocol Master Ver1.1 (The mean of two lowest platelet counts measured in 8 weeks prior to enrollment. Platelet count that is obtained within 3 days after platelet transfusion will not be used)
- 2) Bone marrow biopsy and aspiration with cytogenetics (M/E ratio, cellularity of bone marrow, reticulin grade (reticulin stain/trichrome stain (Appendix 1)), iron stain, narrative pathology report, cytogenetic report and exploratory test described in section 3.3.4)
- 3) Pregnancy test (excluding male subjects and female subjects underwent oophorectomy or hysterectomy or those who are non-childbearing potential i.e., menstrual periods have been absent for at least 12 months)
- 4) ECOG PS

- 5) Vital signs (systolic blood pressure, diastolic blood pressure and pulse rate)
- 6) Hematology (WBC, RBC, Hb, Ht, MCV, MCH, MCHC, PLT, Ret and WBC with differential count)
- 7) Serum chemistry (TP, ALB, T-Bil, D-Bil, AST, ALT, ALP, LDH, γ -GTP, T-Cho, UA, BUN, Cr, Na, K, Ca, P and Cl)
- 8) Blood iron-related parameters (Fe, TIBC, UIBC, TSAT and ferritin)
- 9) Blood coagulation and fibrinolysis (PT-INR, APTT and D-dimer)
- 10) Folic acid and vitamin B₁₂
- 11) Viral serologies for HIV, hepatitis B and C
- 12) 12-lead ECG
- 13) Flow cytometry of the peripheral blood for GPI-cells

8.2.2 Treatment Period: Week 1 (day of initial administration of AMG531) to Week 8

The following observations and examinations during the period of Week 1 (day of initial treatment with AMG531) through to Week 8 will be conducted on the day of study treatment, as a general rule. In consideration of convenience for subjects and investigational sites, \pm 3 days will be allowed except for the subjects assigned to the AMG531 concentration test group. Subjects on dose interruption will also undergo the same observations and examinations. Serum for the determination of AMG531 concentration can be collected at Week 1, Week 4 and Week 8 as described in [Table 8.2.2-1 Schedule for PK sampling](#).

- 1) Vital signs (systolic blood pressure, diastolic blood pressure and pulse rate)
Timing of measurement: Every week before dosing AMG531 in Week 1 to Week 8
- 2) Hematology (WBC, RBC, Hb, Ht, MCV, MCH, MCHC, PLT, Ret and WBC with differential count)
Timing of measurement: Every week before dosing AMG531 in Week 1 to Week 8
- 3) Serum chemistry (TP, ALB, T-Bil, D-Bil, AST, ALT, ALP, LDH, γ -GTP, T-Cho, UA, BUN, Cr, Na, K, Ca, P and Cl)
Timing of measurement: Every week before dosing AMG531 in Week 1 to Week 8
- 4) Blood iron-related parameter (ferritin)
Timing of measurement: Before dosing AMG531 at Week 1 and Week 5
- 5) Blood coagulation (D-dimer)
Timing of measurement: Before dosing AMG531 at Week 1 and Week 5
- 6) Serum AMG531 concentration

Timing of measurement: Before dosing and 4, 12, 24, 48, 72, 96, and 168 hours after dosing AMG531 at Week 1 and Week 8, and before dosing AMG531 at Week 4. Detailed time point with sampling time window is described in Table 8.2.2-1.

7) Serum TPO concentration

Timing of measurement: Before dosing AMG531 at Week 1

8) Antibodies against AMG531 and TPO

Timing of measurement: Before dosing AMG531 at Week 1 (Additional antibody test can be performed on subjects who show clinical findings suggested of possible antibody formation)

9) Cytokine assay

Timing of measurement: Before dosing AMG531 at Week 1

10) GIMEMA bleeding scale (Appendix 3)

Timing of measurement: Before dosing AMG531 at Week 1

Table 8.2.2-1 Schedule for PK sampling

Study Week	Study date	Time of Collection	
Week 1	Day 1	Before dosing of AMG531	within 2 hours
		After dosing of AMG531	4 hours ± 30 minutes
	12 hours ± 90 minutes		
	24 hours ± 3 hours		
	48 hours ± 3 hours		
	72 hours ± 3 hours		
	Day 2		96 hours ± 3 hours
Day 3		168 hours ± 3 hours	
Day 4			
Day 5			
Day 8 ¹⁾			
Week 4	Day 22	Before dosing of AMG531	within 2 hours
Week 8	Day 50	Before dosing of AMG531	within 2 hours
		After dosing of AMG531	4 hours ± 30 minutes
	12 hours ± 90 minutes		
	24 hours ± 3 hours		
	48 hours ± 3 hours		
	72 hours ± 3 hours		
	Day 51		96 hours ± 3 hours
Day 52		168 hours ± 3 hours	
Day 53			
Day 54			
Day 57 ²⁾			

1) The examination at 168 hours after dosing AMG531 at Week 1 will be conducted before dosing AMG531 at Week 2

2) The examination at 168 hours after dosing AMG531 at Week 8 will be conducted before dosing AMG531 at Week 9

8.2.3 Treatment Period: Week 9 to Week 52

The following observations and examinations during Week 9 through to Week 52 will be conducted on the day of study treatment, as a general rule. In consideration of

convenience for subjects and investigational sites, ± 3 days will be allowed. Subjects on dose interruption will also undergo the same observations and examinations.

- 1) Vital signs (systolic blood pressure, diastolic blood pressure, and pulse rate)
Timing of measurement: Every week before dosing AMG531 at Week 9 through to Week 52
- 2) Hematology (WBC, RBC, Hb, Ht, MCV, MCH, MCHC, PLT, Ret and WBC with differential count)
Timing of measurement: Every week before dosing AMG531 at Week 9 through to Week 52
- 3) Serum chemistry (TP, ALB, T-Bil, D-Bil, AST, ALT, ALP, LDH, γ -GTP, T-Cho, UA, BUN, Cr, Na, K, Ca, P and Cl)
Timing of measurement: Before dosing AMG531 at Week 9, 13, 17, 21, 25, 29, 33, 37, 41, 45 and 49
- 4) Blood iron-related parameter (ferritin)
Timing of measurement: Before dosing AMG531 at Week 9, 13, 17, 21, 25, 29, 33, 37, 41, 45 and 49
- 5) Blood coagulation (D-dimer)
Timing of measurement: Before dosing AMG531 at Week 9, 13, 17, 21, 25, 29, 33, 37, 41, 45 and 49
- 6) Bone marrow biopsy and aspiration with cytogenetics (M/E ratio, cellularity of bone marrow, reticulin grade (reticulin stain/trichrome stain (Appendix 1)), iron stain, narrative pathology report, cytogenetic report and exploratory test described in section 3.3.4).
Timing of measurement: Before dosing AMG531 at Week 25 \pm 2 weeks
- 7) Serum TPO concentration
Timing of measurement: Before dosing AMG531 at Week 9
- 8) Antibodies against AMG531 and TPO
Timing of measurement: Before dosing AMG531 at Week 9, Week 25 and Week 41 (Additional antibody test can be performed on subjects who show clinical findings suggested of possible antibody formation)
- 9) Cytokine assay
Timing of measurement: Before dosing AMG531 at Week 9 and Week 25
- 10) GIMEMA bleeding scale (Appendix 3)
Timing of measurement: Before dosing AMG531 at Week 9 and Week 25

8.2.4 Treatment Period: Week 53 to Week 156

The following observations and examinations during Week 53 through to Week 156 will be conducted on the day of study treatment, as a general rule. In consideration of

convenience for subjects and investigational sites, ± 3 days will be allowed. Subjects on dose interruption or tapering will also undergo the same observations and examinations. For those on dose discontinuation after achieving tri-lineage normal level for 8 consecutive weeks without transfusion according to section 6.1.3.3 will be visiting site in every 2 weeks.

- 1) Vital signs (systolic blood pressure, diastolic blood pressure, and pulse rate)
Timing of measurement: Every week before dosing AMG531 at Week 53 through to Week 156 [For subjects on drug discontinuation: every 2 weeks before dosing AMG531 at Week 53 through to Week 156]
- 2) Hematology (WBC, RBC, Hb, Ht, MCV, MCH, MCHC, PLT, Ret and WBC with differential count)
Timing of measurement: Every week before dosing AMG531 at Week 53 through to Week 156 [For subjects on drug discontinuation: every 2 weeks before dosing AMG531 at Week 53 through to Week 156]
- 3) Serum chemistry (TP, ALB, T-Bil, D-Bil, AST, ALT, ALP, LDH, γ -GTP, T-Cho, UA, BUN, Cr, Na, K, Ca, P and Cl)
Timing of measurement: Every 4 weeks before dosing AMG531 at Week 53 through to Week 156
- 4) Blood iron-related parameter (ferritin)
Timing of measurement: Every 4 weeks before dosing AMG531 at Week 53 through to Week 156
- 5) Blood coagulation (D-dimer)
Timing of measurement: Every 4 weeks before dosing AMG531 at Week 53 through to Week 156
- 6) 12-lead ECG
Timing of measurement: Required only at Week 53 before dosing of AMG531
- 7) Bone marrow biopsy and aspiration with cytogenetics (M/E ratio, cellularity of bone marrow, reticulin grade (reticulin stain/trichrome stain (Appendix 1)), iron stain, narrative pathology report, cytogenetic report and exploratory test described in section 3.3.4).
Timing of measurement: Before dosing AMG531 at Week 53, Week 77, Week 105, Week 129. ± 2 weeks will be allowed.
- 8) Serum TPO concentration
Timing of measurement: Before dosing AMG531 at Week 53, Week 105
- 9) Antibodies against AMG531 and TPO
Timing of measurement: Before dosing AMG531 at Week 57, Week 77, Week 105, Week 129 (Additional antibody test can be performed on subjects who show clinical findings suggested of possible antibody formation)
- 10) GIMEMA bleeding scale (Appendix 3)
Timing of measurement: Before dosing AMG531 at Week 53, Week 77, Week 105, Week 129

8.2.5 End of treatment: one week after last administration of AMG531

All subjects who completed the study treatment will undergo the following observations, assessments and examinations one week after the last administration of AMG531. In consideration of convenience for subjects and investigational sites, ± 3 days will be allowed.

Subjects exposed to AMG531 but terminated the study treatment earlier than scheduled will undergo the same observations, assessments and examinations one week after their last administration of AMG531. In consideration of convenience for subjects and investigational sites, ± 3 days will be allowed.

- 1) Vital signs (systolic blood pressure, diastolic blood pressure, and pulse rate)
- 2) Hematology (WBC, RBC, Hb, Ht, MCV, MCH, MCHC, PLT, Ret and WBC with differential count)
- 3) Serum chemistry (TP, ALB, T-Bil, D-Bil, AST, ALT, ALP, LDH, γ -GTP, T-Cho, UA, BUN, Cr, Na, K, Ca, P and Cl)
- 4) Blood iron-related parameter (ferritin)
- 5) Blood coagulation (D-dimer)
- 6) Bone marrow biopsy and aspiration with cytogenetics (M/E ratio, cellularity of bone marrow, reticulin grade (reticulin stain/trichrome stain (Appendix 1)), iron stain, narrative pathology report, cytogenetic report and exploratory test described in section 3.3.4) (to be exempt for the patient withdrawn from the study within 11 weeks from the last bone marrow examination). Time window ± 2 weeks will be allowed.
- 7) Serum AMG531 concentration (only at withdrawal in Week 8 or earlier)
- 8) Serum TPO concentration
- 9) Cytokine assay (To be required only for the patients withdrawn from the study before Week 53)
- 10) GIMEMA bleeding scale (Appendix 3)
- 11) 12-Lead ECG

8.2.6 End of study: four weeks after last administration of AMG531

All subjects should complete an end of study visit four weeks after their last administration of AMG531. In consideration of convenience for subjects and investigational sites, ± 3 days will be allowed.

Subjects exposed to AMG531 but terminated the study treatment earlier than scheduled will undergo the same observations, assessments and examinations four weeks after their last administration of AMG531. In consideration of convenience for subjects and investigational sites, ± 3 days will be allowed.

- 1) Vital signs (systolic blood pressure, diastolic blood pressure, and pulse rate)
- 2) Hematology (WBC, RBC, Hb, Ht, MCV, MCH, MCHC, PLT, Ret and WBC with differential count)
- 3) Serum chemistry (TP, ALB, T-Bil, D-Bil, AST, ALT, ALP, LDH, γ -GTP, T-Cho, UA, BUN, Cr, Na, K, Ca, P and Cl)
- 4) Blood iron-related parameter (ferritin)
- 5) Blood coagulation (D-dimer)
- 6) Antibodies against AMG531 and TPO

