3.3.1.2 Secondary endpoints

- The proportion of subjects achieving a platelet response any time during the initial dose evaluation period, Week1 through Week 12, Week 1 through Week 16, Week 1 through Week 24, and Week 1 through Week 52.
- The proportion of subjects who become platelet transfusion independent during the initial dose evaluation period, Week1 through Week 12, Week 1 through Week 16, Week 1 through Week 24, Week 1 through Week 52, Week 1 through Week 104, and Week1 through Week 156
- The proportion of subjects achieving erythroid response and/or neutrophil response during the initial dose evaluation period, Week1 through Week 12, Week 1 through Week 16, Week 1 through Week 24, Week 1 through Week 52, Week 1 through Week 104, and Week1 through Week 156
- Duration of platelet response
- Time to platelet response
- Changes in platelet count, hemoglobin concentration, and neutrophil count as continuous variables
- Changes in bone marrow cellularity and reticulin grade
- Changes in GIMEMA bleeding scale
- The proportion of subjects achieving tri-lineage responses
- The proportion of subjects able to discontinue study drugs after achieving normal level for 8 consecutive weeks without transfusion.
- Duration of study drug discontinuation while maintaining stable response

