9 ADVERSE EVENTS

9.1 Definition of adverse events

An adverse event (AE) is herein defined as any untoward medical occurrence in subjects received AMG531. An AE can therefore be any unfavorable or unintended sign (including an abnormal laboratory finding), symptom or disease, regardless of causal relationship to AMG531. An adverse drug reaction (ADR) is defined as any AE of which causal relationship to AMG531 cannot be ruled out (any events assessed to be other than “unlikely” or “not related”).

Laboratory results (hematology, serum chemistry, blood iron-related parameters, blood coagulation and fibrinolysis) will be evaluated for deviations (abnormalities) from normal range of each investigative site. In the event of an abnormal value (abnormal change), clinical significance of the abnormal change in comparison with baseline will be assessed. In consideration of pharmacological effects of AMG531, an increase in platelet, hemoglobin, reticulocyte, and/or neutrophil will be treated as abnormal only in the cases where the investigator considers it to be medically important.

For signs, symptoms, and abnormal laboratory findings associated with a disease (diagnosed disease), the disease will be treated as an AE. If any atypical sign is observed in that disease, the sign will be treated as an individual AE.

Observation period of both non-serious and serious adverse events will be the period between the start of study treatment through to the end of study visit or 4 weeks after the last administration of AMG531, whichever is longer. However, any event reported as delayed toxicity or the like attributed the investigational product will be treated as an adverse event as well.

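### For subjects tapered off AMG531, the end-of-study visit and adverse-event window close about 4 weeks after the last dose, yet 2-weekly visits run to Week 156

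*Combined protocol and SAP*

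**What the plan says.** **End of study.** Section 8.2.6: "All subjects should complete an end of study visit four weeks after their last administration of AMG531", with ±3 days allowed. Schedule footnote 9 repeats the anchor and makes one exception, for safety withdrawals who cannot attend the planned visit.

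**End of treatment.** Section 8.2.5: "All subjects who completed the study treatment will undergo the following observations, assessments and examinations one week after the last administration of AMG531". The same visit applies to subjects who end treatment earlier than scheduled. Footnote 8 uses the same 1-week anchor.

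**Adverse events.** Section 9.1 observes serious and non-serious events from the start of treatment "through to the end of study visit or 4 weeks after the last administration of AMG531, whichever is longer". It adds that "any event reported as delayed toxicity or the like attributed the investigational product will be treated as an adverse event as well".

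**Off-drug follow-up.** Section 6.1.3.3 creates a group that stops drug by design. These subjects stay off while a stable response holds, and dosing can be resumed if counts fall. Section 8.2.4 sets vital signs and hematology for them: "For subjects on drug discontinuation: every 2 weeks before dosing AMG531 at Week 53 through to Week 156". Footnote 11 puts them on 2-weekly visits, and footnote 12 says dosing is skipped.

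**Endpoint.** Section 3.3.1.2 lists as a secondary endpoint "Duration of study drug discontinuation while maintaining stable response". Section 12.1.1.2 summarises the longest such period descriptively.

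**The concern.** A subject who tapers off and stays off has a last administration well before Week 156. Section 8.2.6 then makes the end-of-study visit due 4 weeks later, while 8.2.4 still has the subject attending every 2 weeks. No text says which governs. Because dosing may resume, the site also cannot know at the time of stopping which dose will prove to be the last.

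The main consequence is for safety data. Both limits in 9.1 depend on the last dose, so an infection, bleed or thrombosis after the literal window, if non-fatal and not attributed to the product, would not be a study adverse event even when it is reported at a scheduled visit. Sites could reasonably apply different rules to the same kind of subject.

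A lesser consequence concerns the off-drug duration endpoint. Stable response requires freedom from transfusion, and Section 6.2.3 records transfusions to the end of the study. If the end-of-study visit is placed at 4 weeks, it is unclear whether that recording, and follow-up for the endpoint, continue.

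**Working it through.** The plan gives no figure for this, and no alpha, power or effect size is involved. The check is calendar arithmetic on the protocol's own rules.

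**Inputs**
- Normal-level run before tapering: 8 weeks at one dose (6.1.3.3).
- Taper step: one level every 4 weeks; stop after 4 weeks at the lowest level (6.1.3.3).
- Levels: 3, 6, 10, 13, 16 and 20 µg/kg (Table 6.1.3-1).
- End of study: last dose + 4 weeks, ±3 days (8.2.6).
- End of scheduled off-drug visits: Week 156, on odd-numbered weeks (8.2.4, footnote 11).

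**Assumptions.** The 8-week run is counted from Week 53. Tapering is uninterrupted, with no dose holds. A subject already on the lowest level completes the 8-week run, as footnotes 11 and 12 describe. The subject does not resume dosing.

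**Formulas.** Let *i* be the number of levels above the lowest at entry.
- Last-dose week L = 53 + 8 + 4*i* − 1 = 60 + 4*i*
- End-of-study week E = L + 4
- Scheduled weeks beyond the window = 156 − E

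| Level at Week 53 (µg/kg) | i | L | E | 156 − E | 2-weekly visits after E |
|---|---|---|---|---|---|
| 3 | 0 | 60 | 64 | 92 | 46 |
| 6 | 1 | 64 | 68 | 88 | 44 |
| 10 | 2 | 68 | 72 | 84 | 42 |
| 13 | 3 | 72 | 76 | 80 | 40 |
| 16 | 4 | 76 | 80 | 76 | 38 |
| 20 | 5 | 80 | 84 | 72 | 36 |

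The off-drug time from last dose to Week 156 is 156 − 60 = 96 weeks down to 156 − 80 = 76 weeks. The share beyond the literal window is 92/96 = 95.8% down to 72/76 = 94.7%.

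**Sensitivity.** If the 8-week run may be accrued in Weeks 45 to 52, every L and E falls 8 weeks earlier and the remaining time becomes 100 to 80 weeks.

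**Where the conflict ends.** It disappears when L + 4 ≥ 156, that is, for a last dose at Week 152 or later. A subject still on drug at Week 156 has end of study at Week 160 and no conflict.

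**Does the longer-of-two clause in 9.1 help?** With the end-of-study visit held inside its window, day 25 to 31 after the last dose, the later of that visit and day 28 is day 28 to 31. The clause extends collection materially only if the visit is held outside the window that 8.2.6 allows.

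**The case against.** The strongest reply is that 8.2.4 is the specific provision and so governs. It treats off-drug subjects as still within the treatment period, footnote 12 speaks of skipped dosing, and dosing can resume. On that view a last administration cannot be identified when a taper ends, and 8.2.5 arguably does not reach such a subject, who has neither completed treatment nor ended it early. This is a fair account of the likely intent. It does not remove the conflict, because 8.2.6 says all subjects and has no exception for this group.

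On adverse events, 9.1 follows the end-of-study visit if that visit is later, so a visit held after Week 156 would carry collection to that date. It would, however, breach the ±3 days in 8.2.6, and Section 15 does not permit planned departures of this kind. Section 10.3 promises adverse-event monitoring throughout the study period, but as a general statement it does not define the window. The Section 8.1 schedule table could not be read in the public text, only some of its footnotes, so an adverse-event row there cannot be ruled out.

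The two limits in 9.1 are not always the same date. The visit window, and the early visit that 11.1.2 allows after a safety withdrawal, give the longer-of-two wording a real function.

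A reader might infer that off-drug duration cannot exceed 4 weeks, or that loss of response and clonal change would go unseen. The documents do not support either. Section 8.2.4 schedules off-drug hematology every 2 weeks to Week 156, and marrow with cytogenetics at Weeks 77, 105 and 129 without an off-drug exemption. Section 8.2.7 surveys survival, cytogenetics, fibrosis, AML/MDS and transplantation at about 3 years. Neither endpoint passage sets a cap. The absence of a censoring rule for a descriptive summary is detail that 12.5 leaves to the statistical analysis plan.

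**Conclusion.** The contradiction is real and confined to subjects who stop drug through tapering under 6.1.3.3, do not resume, and have their last dose before Week 152. Loss of data is conditional: it follows if 8.2.6 is applied as written and 9.1 with it, not if 8.2.4 is taken to govern. The data exposed are mainly adverse events that are not attributed to the product and lie outside the 8.2.7 list.

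The 92 to 72 weeks are ceilings under the stated tapering assumptions, not an expected loss per subject. The number affected is unknown: it is the part of the 32 who enter long-term treatment, hold normal levels in all three lineages and taper off. The off-drug duration endpoint has an ambiguous end of follow-up on the literal reading, but its data are scheduled. The Week 9 primary endpoint is unaffected. The wording should be corrected, but the point does not threaten the trial's main result.

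**What to change.** Reconcile 8.2.5, 8.2.6, 9.1 and schedule footnotes 8 and 9 with 8.2.4, footnotes 11 and 12, and 6.1.3.3, so that a subject off drug after tapering has one stated end-of-study anchor. State in 9.1 that adverse-event observation for these subjects runs through the last protocol visit attended, or 4 weeks after the last administration if that is later. Transfusion recording under 6.2.3, which runs to the end of the study, would then follow the same anchor.

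The cost is wording in a few sections and footnotes, plus adverse-event entry at visits already scheduled. No visit is added, and no dose or clinical rule changes.
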